### **1.2. SECONDARY ANALYSES**

The analysis of secondary endpoints and exploratory variables (see section **Fehler! Verweisquelle konnte nicht gefunden werden.**) including the total number of recurrent HF hospitalizations, weight loss during index hospitalization, duration of index hospitalization (in days), changes in laboratory measurements (e.g. resolution of congestion) as well as "Quality of Life" (short form of KCCQ with EQ-5D as standardized measure of health status) and Patient Global Assessment (PGA) will included in formal analyses. There will be no structured analysis taking into account multiple testing. Summary statistics such as mean, standard deviation [SD], median, 25th [Q1] and 75th [Q3] percentiles, minimum [Min] and maximum [Max]) will be calculated for continuous variables. Frequencies and percentages will be presented for categorical variables.

The comparison between treatment groups will be evaluated using logistic regression analysis adjusting for stratification variables (other than study site) or Fisher's exact test (in case of a rare outcome) for categorical variables, using joint modeling of death and recurrent events in the case of heart failure hospital admissions and linear regression analysis for continuous variables adjusting for stratification variables (other than study site) and, where appropriate for baseline levels of the variable. Non-parametic methods will be used where appropriate.

As described in section 1.1, patients who die or lost to follow-up after discharge are included in all secondary analyses with all available data up to the date of last contact.

Descriptive summaries of KM curves will be presented for all-cause mortality. Patients alive at the end of the study will be censored at the last date known to be alive.

More detailed descriptions of statistical methods and assumptions including calculated variables and the proposed format and content of tables and figures in the final report will be detailed in the Statistical Analysis Plan (SAP). Wherever reasonable, evaluation will be stratified by subgroups (i.e. age, other baseline characteristics) and pre-defined in the SAP. All statistical analyses will be performed using the software package SAS® [SAS Institute Inc., The SAS system for Windows, Cary, NC: SAS Institute Inc., 2013].

### **1.3.** SAFETY ANALYSES

Standard procedures for reporting of adverse events will be used. Adverse events will be summarized as frequencies and percentages by treatment group.

### **1.4.** FURTHER STATISTICAL CONSIDERATIONS

### Sensitivity analysis

For sensitivity and robustness, the analyses of the primary and secondary endpoints will be repeated for the Per-Protocol-Population.

### Handling of missing data

We will perform multiple imputation for subjects with missing data on the primary and secondary outcomes at 90 days, if applicable (details will be specified in the SAP).

### **1.5.** ANALYSIS SETS

For this study, the following analysis populations will be defined:

### Per-protocol-population (PP)

Includes all subjects who entered the study in accordance with both the inclusion / exclusion criteria without major protocol deviations and who finished the study in accordance with the study protocol.

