### Target variables:

Primary endpoint:

Composite endpoint of cardiovascular mortality in 90 days after randomization and heart failure events in 90 days after discharge. HF events are defined as HF rehospitalization or an urgent HF visit.

Secondary endpoints:

- 1. Heart failure rehospitalization analyzed as a recurrent event in 90 days after discharge
- 2. Time until first HF rehospitalization in 90 days after discharge
- 3. Time until first urgent HF visit in 90 days after discharge
- Quality of life (Patient Global Assessment at baseline, discharge, FU30, FU90; Short Kansas City Cardiomyopathy Questionnaire and EQ-5D-5L at discharge, FU30, FU90)
- 5. Days alive and out of hospital up to 90 days after discharge
- 6. Cardiovascular mortality in 90 days after randomization
- 7. Resolution of congestion defined as at least two of the final eligibility criteria present at randomization have resolved (this does not include chest x-ray criterion, i.e. if x-ray criterion was one out of two final eligibility criteria, only resolution of the other criterion necessary), thus:
  - Jugular venous pressure of <8cm H2O
  - No orthopnea
  - Trace or no peripheral edema
  - Respiratory rate no longer  $\geq$  20/minute
- 8. In-hospital worsening heart failure until discharge
- 9. Weight loss at 96h after randomization and at discharge

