### Safety-population (SP)

Includes all subjects who were randomized.

Assignment of patients to analysis populations will be done during the data review meeting. Primary analysis will be based on the ITT population; an additional analysis on PP will be performed to assess validity of results. Safety analyses will be performed on the SP.

The primary endpoint measured at 90 days will be analyzed on an intention to treat basis. It is anticipated that there may be some "crossover" from the intervention group to the control group or from the control group to the intervention group. The number of crossovers will be documented to provide context for interpreting the primary results; however, treatment crossovers will be analyzed according to the intention to treat principle and thus will be included in the arm to which they were randomized.

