### **1.6.** SAMPLE SIZE JUSTIFICATION

Previously published results from clinical trials comparing intravenous loop diuretics to mechanical fluid removal by isolated veno-venous ultrafiltration have yielded conflicting results regarding heart failure-related rehospitalization. The present PURE-HF study is similar to the AVOID-HF (Costanzo et al., 2015) in terms of study design and targets. The primary objective of the AVOID-HF study was to determine whether UF prolonged the time to first HF event within 90 days of hospital discharge. Regarding sample size considerations, the AVOID-HF trial refers to different publications in order to provide an estimate of the combined HF event rate for the control group and the assumed reduction of the HF event rate in the UF group (Felker et al., 2011, O'Connor et al., 2011, Costanzo et al., 2007, Konstam et al., 2007, Hernandez et al., 2010, Ross et al., 2010).

Taking into account the assumptions and observations actually made in the prematurely terminated AVOID-HF study published by Costanzo et al. (Costanzo et al., 2016) we estimated that 864 patients (432 in each arm) should be sufficient to test whether there is a difference between the event proportions of the test and the control treatment. The proposed sample size calculations based on the two-sided Z test with unpooled variance and include the following assumptions: 1)  $\alpha$  of 0.05 ( $\alpha$ /2=0.025); 2) power (1- $\beta$ ) of 0.90; 3) an HF event rate for the loop diuretics group of 25% plus 2% cardiovascular death and 4) a reduction of the event proportion for the UF group of 37,5 % (this leads to an event proportion for the UF group of 16,88%). The estimated total sample size is displayed with additional patients included to account for 10% of subjects lost to follow-up and 13% treatment failures due to crossover during the treatment period

Event proportion			Sample size N		
control group	UF group	Reduction	Crude	Incl. 10% loss to FU	Incl. 10% loss to FU and 13% treatment failure
27.00%	16.88%	37.50%	694	764	864

- 1) Test for two proportions,
- 2) two-sided a of 0.05,
- 3) power of 0.90,
- 4) HF event rate of control group of 25% + 2% in-hospital death
- 5) an event proportion for the loop diuretics group (control group) of 27%,
- 6) an event proportion for the UF group (treatment group) of 16.88% (37.50% reduction),
- 7) including 10% loss to follow up and 13% crossover (i.e. treatment failure),

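### The per-protocol set requires patients to have finished the study and does not say that death counts as finishing, so the per-protocol repeat of an endpoint containing CV death may lose the deaths

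*Combined protocol and SAP*

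**What the plan says.** Combined protocol and SAP, section 1.5, Per-protocol-population: besides meeting the entry criteria and having no major deviations, a patient must be one "who finished the study in accordance with the study protocol". Finishing is thus a separate condition, added to eligibility and the absence of major deviations. It is not defined for a patient who dies.

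The set has a stated job. Under Sensitivity analysis in 1.4, "the analyses of the primary and secondary endpoints will be repeated for the Per-Protocol-Population". At the end of 1.5, "an additional analysis on PP will be performed to assess validity of results". The same paragraph makes ITT the basis of the primary analysis.

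The primary endpoint (synopsis, Target variables) is a "Composite endpoint of cardiovascular mortality in 90 days after randomization and heart failure events in 90 days after discharge". CV mortality within 90 days of randomization is also secondary endpoint 6.

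Two other places bear on deaths. Section 1.1 censors follow-up time at death in the descriptive time-to-event displays. Section 1.2 says that "patients who die or lost to follow-up after discharge are included in all secondary analyses with all available data" up to last contact. Neither defines membership of the PP set. On that, 1.5 says only: "Assignment of patients to analysis populations will be done during the data review meeting".

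**The concern.** In ordinary usage, a patient who dies during follow-up has not finished the study. On that reading, membership of the PP set depends on an outcome that the set is used to check.

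The two time windows sharpen this. CV mortality is counted to 90 days after randomization, while HF follow-up runs to 90 days after discharge, which comes later. Anyone who completes follow-up is therefore alive at day 90 after randomization. Secondary endpoint 6 repeated in such a PP set would be zero in both arms and would tell the reader nothing.

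For the composite, each arm would lose the patients whose event was death. A treatment that shifted events from HF admissions to deaths would look better in PP than in ITT. That is the case in which a check on validity matters most. If the literal reading is not intended, nothing replaces it, and deaths would be classified at a meeting held after they have occurred.

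**Working it through.** **Inputs from section 1.6.** Control: 25% HF events plus 2% CV death, 27% in total. Reduction 37.5%, so UF = 0.27 × 0.625 = 0.16875 (printed as 16.88%). "two-sided a of 0.05", power 0.90, Z test with unpooled variance, 432 per arm. The documents give no UF death rate, so every UF death rate below is an assumption.

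**The plan's own figure.** n per arm = (1.960 + 1.2816)² × [0.27 × 0.73 + 0.1688 × 0.8312] / (0.27 − 0.1688)² = 346.2, so 347 per arm and 694 in total. Then 694 × 1.10 = 763.4, giving 764, and 764 × 1.13 = 863.3, giving 864. The plan's 694 / 764 / 864 reproduce, and this point does not dispute them.

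**Effect of dropping deaths.** Let p be the composite proportion in an arm and d the proportion whose only event is CV death. The plan adds 25% and 2%, so it treats the two as disjoint.

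- PP proportion = (p − d) / (1 − d)
- PP odds = (p − d) / (1 − p), because the factor 1 − d cancels
- PP odds ratio = ITT odds ratio × [(p_UF − d_UF) / p_UF] ÷ [(p_C − d_C) / p_C]

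So the odds ratio is unchanged exactly when deaths make up the same share of events in both arms.

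**Planned totals.** With deaths kept, the odds ratio is (0.16875/0.83125) / (0.27/0.73) = 0.549. With deaths dropped, control is 0.25/0.98 = 25.5%, and 432 × 0.02 = 8.64, about 9 control patients, leave. Control odds become 0.25/0.73. For UF:

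| Assumed UF CV death | PP proportion, UF | PP odds ratio |
|---|---|---|
| 0% | 0.16875 = 16.9% | (0.16875/0.83125) / (0.25/0.73) = 0.593 |
| 1.25% (proportional: 2% × 0.625) | 0.15625/0.9875 = 15.8% | (0.15625/0.83125) / (0.25/0.73) = 0.549 |
| 2% (same as control) | 0.14875/0.98 = 15.2% | (0.14875/0.83125) / (0.25/0.73) = 0.523 |
| 4% | 0.12875/0.96 = 13.4% | (0.12875/0.83125) / (0.25/0.73) = 0.452 |

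Here the composite totals are held at the planned values, so more UF deaths imply fewer UF patients with HF events only.

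**No true effect on the composite, more deaths under UF (assumed).** HF events 25% vs 20%, CV death 2% vs 7%.

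- True composite: 27% vs 27%, odds ratio 1.00
- PP without deaths: 0.25/0.98 = 25.5% vs 0.20/0.93 = 21.5%
- PP odds ratio: (0.20/0.73) / (0.25/0.73) = 0.80

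**Not counted.** The literal reading would also remove patients who die of non-CV causes and those who have an HF event and later die. The documents give no rates for either.

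**The case against.** The strongest reply is that the documents nowhere exclude deaths from PP. A patient followed according to protocol until a protocol-defined endpoint event can be said to have finished according to protocol. Section 1.2 keeps patients who die after discharge in all secondary analyses, and 1.4 repeats those analyses in PP, which weighs against presuming that deaths are dropped. Section 1.2 also defers detail to a SAP. This stands to the extent that exclusion of deaths is the literal reading and not an express rule.

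It does not remove the problem. The sentence in 1.2 concerns use of data, not set membership. It covers deaths after discharge only and does not address the primary endpoint. The numbered assumptions in 1.6 label the planned 2% as deaths in hospital (the text above them calls it cardiovascular death), and patients who die in hospital never enter post-discharge follow-up. If 1.2 is meant to keep deaths in PP, it conflicts with the plain wording of 1.5. Either way the text needs an edit.

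A second reply is that little is at stake: PP is supportive, 1.5 also provides a multiple-imputation sensitivity analysis, and excess deaths would show in CV mortality under ITT and in the all-cause mortality curves. That is correct, and it limits the weight of the point. A third is that the example with 7% deaths builds in its result. It does. It shows what the rule can do and is not a forecast; nothing in the documents suggests such an imbalance.

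**Conclusion.** The point holds as a defect in the PP definition. Read literally, the completion condition makes membership depend on a component of the primary endpoint and empties the PP analysis of CV mortality. Read otherwise, deaths are handled without a rule.

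The size is modest under the plan's own assumptions. About 9 control patients leave, and the odds ratio stays at 0.549 if UF deaths fall in proportion. It shifts slightly, to 0.523, if deaths are 2% in both arms, and ranges from 0.593 to 0.452 over assumed UF death rates of 0 to 4%. It becomes misleading when deaths differ materially between arms, as in the assumed example where a true odds ratio of 1.00 appears as 0.80.

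A reader might infer more than this, and the documents do not support it. They do not state that deaths will be excluded. The 1.25% UF death rate is an assumption and not a planned figure. The primary result is not biased by this wording, because it rests on ITT.

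**What to change.** In 1.5, delete the completion condition. Define PP by eligibility and absence of major protocol deviations up to death or the end of follow-up, whichever comes first. State that death, before or after discharge, is not a reason for exclusion from PP. Handle loss to follow-up in PP by the same missing-data rule as in ITT, whether or not the patient has already had an event.

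The last clause matters. It would be easy to repair the text by counting patients with a primary event as completers. That would keep a patient who has an early HF event and is then lost, yet drop an event-free patient lost at the same time, so membership would again depend on outcome.

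The cost is a few sentences, settled before patients are assigned to sets. No new data are needed, and the primary analysis and the sample size do not change.

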### (Modified) Intention-to-treat population (ITT=FAS)

Includes all subjects who were randomized and for whom complete efficacy data are available. We will analyze subjects lost to follow up based on subjects' status at time of withdrawal of consent and add a sensitivity analysis using multiple imputation for those with missing outcomes at 90 days.

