### 1. STATISTICS

### **1.1. PRIMARY ANALYSIS**

The primary endpoint of the trial is the composite of cardiovascular mortality in 90 days after randomization or a heart failure event in the 90 days after discharge.

The primary analysis of the effectiveness of the UF treatment will be conducted in the ITT population (see section 1.5). The occurrence of cardiovascular deaths or heart failure event after discharge from hospital will be summarized using event proportions, i.e. number of patients with an event divided by the number of patients randomized to the respective treatment group.

The null hypothesis of no difference in event proportions between the randomized groups will be tested in a two sided test using logistic regression analysis adjusting for stratification variables (other than study site). Odds ratios including 95% confidence intervals (CI) will be presented as well as p-values (Wald methodology). In addition, descriptive analyses of the components of the primary outcome will be reported in the form of Kaplan-Meier (KM) curves for the time-to-event for each of cardiovascular mortality in 90 days after randomization and heart failure event within 90 days after discharge (Kaplan and Meier, 1958). Follow-up times will be censored at date of death, loss to follow-up or at the 90 day cut-off period.

Hazard ratios comparing the two treatment groups under study will be determined within the Cox proportional hazard model and provided along with the 95% HR confidence limits (Wald-CI).

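### On its natural reading, the primary test counts patients lost early without an event as 90-day non-events, which biases the odds ratio if loss differs by arm; the analysis set and the denominator also conflict

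*Combined protocol and SAP*

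**What the plan says.** Four statements in the combined protocol and SAP bear on patients whose 90-day status is unknown.

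- **Section 1.1, primary analysis.** The outcome is summarized as the "number of patients with an event divided by the number of patients randomized to the respective treatment group". The test is a logistic regression on event yes/no, adjusted for stratification variables other than site. It makes no use of follow-up time.
- **Section 1.5, modified ITT set, second sentence.** "We will analyze subjects lost to follow up based on subjects' status at time of withdrawal of consent". The same sentence adds multiple imputation as a sensitivity analysis.
- **Section 1.5, modified ITT set, first sentence.** The set holds randomized subjects whose efficacy data are complete.
- **Section 1.4, missing-data paragraph.** "We will perform multiple imputation for subjects with missing data on the primary and secondary outcomes at 90 days, if applicable". The specifics are left to the SAP, and the role of the imputation (primary or sensitivity) is not stated.

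The composite endpoint counts cardiovascular death up to 90 days after randomization and heart failure (HF) events in the 90 days after discharge.

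**The concern.** A yes/no model without follow-up time can take a patient's status at withdrawal in only one way: no event so far means no event. Someone who withdraws in hospital on day 3 is then recorded as event-free through a post-discharge window that never began. In effect this is single imputation of success, treated as if it had been observed.

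This endpoint is particularly exposed. HF events count only after discharge, and section 1.6 attributes 25 of the 27 control-arm points to them. For a patient lost before discharge, at least 25/27 = 93% of the expected events therefore fall after the loss.

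The odds ratio and p-value that decide the trial would depend partly on how many patients leave each arm, and when. The rule is also worded for withdrawal of consent but applied to everyone lost to follow-up, so patients who simply disappear have no clear reference date. Because the completeness condition points to a different analysis, and populations are assigned at the data review meeting, the choice between the two readings is not fixed in advance.

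**Working it through.** **Inputs from section 1.6.** Two-sided alpha 0.05; power 0.90; control 27%; UF 16.88% (27% × 0.625 = 16.875%); 432 per arm; 10% loss to follow-up, not split by arm; 13% crossover; sizing by a "two-sided Z test with unpooled variance".

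**Reproducing the plan's sample size.** n per arm = (1.960 + 1.282)² × [p1(1 − p1) + p2(1 − p2)] / (p1 − p2)².
- With p2 = 0.16875, n = 345.8, so 346 per arm or 692 in total.
- With p2 rounded to 0.1688, n = 346.2, so 347 per arm or 694, the plan's figure.
- Inflation: 694 × 1.10 = 763.4, so 764; 764 × 1.13 = 863.3, so 864. Both match the plan.

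**Model for the status-at-withdrawal rule.** Let w be the share of an arm that is lost and m the share of lost patients' events that fall after the loss. Then

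observed proportion = p × (1 − w × m).

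Neither w by arm nor m is in the documents. The splits below are assumptions that average 10%, and m is shown at 0.5 and 1. Tests use the unpooled Z approximation with 432 per arm, not the adjusted logistic model, and crossover is ignored.

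**No true effect (27% in both arms), loss 5% control v 15% UF**
- m = 0.5: 0.27 × 0.975 = 0.2632 v 0.27 × 0.925 = 0.2498. Difference 1.35 points, odds ratio 0.93, z shift 0.45, two-sided error 7.4%.
- m = 1: 0.27 × 0.95 = 0.2565 v 0.27 × 0.85 = 0.2295. Difference 2.7 points, odds ratio 0.86, z shift 0.93, two-sided error 15%.

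**Planned effect, reversed loss (15% control v 5% UF)**
- Without loss: difference 10.1 points, power about 95%.
- m = 0.5: 0.2498 v 0.1645. Difference 8.5 points, power 87%.
- m = 1: 0.2295 v 0.1603. Difference 6.9 points, power 73%.

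**Equal loss, 10% in each arm**
- No true effect, m = 1: 24.3% v 24.3%. No bias.
- Planned effect, m = 0.5: 0.2565 v 0.1603. Difference 9.6 points, odds ratio 0.553, power 94%.
- Planned effect, m = 1: 0.2430 v 0.1519. Difference 9.1 points, odds ratio 0.558, power 92%.
- The odds ratio without loss is 0.549.

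**The other reading.** If the completeness condition is taken literally, lost patients leave the analysis. With 10% loss, 432 × 0.90 = 389 per arm remain and power is about 93%, again ignoring crossover. Loss unrelated to risk then causes no bias even when it is unequal, but the denominator in section 1.1 is no longer all randomized. The two readings cannot both be followed.

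**The case against.** **The plan may not score lost patients as successes.** The completeness condition, taken literally, removes them from the set, and the error rates above then do not apply. This stands as a limit on the figures. It does not rescue the plan, because that reading contradicts the all-randomized denominator and leaves the status-at-withdrawal sentence with nothing to act on.

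**Other planned analyses would expose the problem.** Multiple imputation is planned as a sensitivity analysis, and section 1.1 adds Kaplan-Meier curves censored at loss to follow-up, together with Cox hazard ratios. This is fair mitigation. However, none of these replaces the logistic test, and the text does not say what follows if they disagree with it.

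**The size rests on an assumed split.** This is correct. Section 1.6 gives only the overall 10%. A reader might infer that the rule favours UF, or that the trial as planned has an inflated false-positive rate. The documents support neither: no loss by arm is given, the bias can go either way, and equal loss produces none under the null. The text does not use the term open-label. That unequal withdrawal is plausible is an inference from comparing 1–7 UF sessions of 6–10 hours with diuretics, with no sham described.

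**Sections 1.4 and 1.5 do not conflict over imputation.** A reader might infer that they contradict each other. They do not: section 1.4 leaves the role open and section 1.5 gives it a sensitivity role.

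**Imputation is not a cure.** Under missing-at-random it corrects unequal loss only if lost patients resemble those who stay, given the variables in the model. This stands, and the fix allows for it.

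**Conclusion.** The point holds in a conditional form. On the natural reading of sections 1.1 and 1.5, event-free patients who are lost enter the primary test as 90-day non-events, and the odds ratio is biased when loss differs by arm, in whichever direction the loss runs. Under an assumed 5% v 15% split, with half to all of the lost patients' events missed, the false difference with no true effect is 1.35 to 2.7 points and the error is 7.4% to 15%. In the opposite direction, with the planned effect true and all events missed, power falls from about 95% to 73%. With equal 10% loss the odds ratio moves only from 0.549 to at most 0.558.

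Independently of any assumed split, the completeness condition and the all-randomized denominator are incompatible. The plan should settle the analysis set, the denominator and the rule for unknown outcomes together.

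**What to change.** 1. In section 1.5, define the ITT set as all randomized patients and delete the completeness condition.
2. Make the multiple-imputation logistic regression the primary analysis. Observed events stay events. For event-free patients who are lost, whether or not they withdrew consent, impute the unobserved part of the window from arm, stratification variables and time of loss.
3. Keep status at withdrawal as a sensitivity analysis.
4. Add a tipping-point analysis, because missing-at-random may fail. This matters most for patients lost in hospital, whose whole post-discharge window would be imputed.
5. Reword sections 1.1, 1.4 and 1.5 to agree, before database lock.

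The cost is mainly wording, since the imputation and the status-at-withdrawal analysis are both already planned; the tipping-point analysis is a small addition. The downsides are a slightly wider confidence interval and a primary result that rests on a missing-at-random assumption.
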